The patients who receive only one dose due to anaphylaxis (grade 3 or 4) or seizure will be removed from the evaluation of all objectives. The anticipated rate of each toxicity is about 1%. However, the descriptive statistics will be calculated for these patients who receive only one dose, e.g., adverse events and endpoints in all the objectives. The expected accrual number for our study will be 39 patients (to yield 38 evaluable subjects).

Unacceptable toxicities consist of acute kidney injury (defined by doubling of creatinine) or anaphylaxis (grade 3 or 4) or thrombotic event or seizure. The anticipated rate of each toxicity is about 1%. Thrombotic events occurring six weeks beyond the time of surgery will not be considered related to TXA administration. A heuristic approach is used to monitor each of the three toxicities in the TXA group. For each toxicity, starting from the 3rd patient, if the number of patients with any toxicity is equal to or larger than 3, the study accrual will be paused and amendments to the protocol will be discussed with the IRB. This monitoring rule yields the largest type-I error rate 0.044 when the 20th (one patient is removed due to not receiving the 2nd dose) patient show the toxicity (the 20th patient and any two previous patients in the TXA group).

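### The toxicity pausing rule in Section 11.1 reads mostly as one rule per toxicity at 1%, but its stated type-I error of 0.044 belongs to a rule pooling all four toxicities at 4%

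*Combined protocol and SAP*

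**What the plan says.** Everything at issue stands in the toxicity-monitoring paragraph of Section 11.1 of the combined protocol and SAP.

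- **The list has four items.** "Unacceptable toxicities consist of acute kidney injury (defined by doubling of creatinine) or anaphylaxis (grade 3 or 4) or thrombotic event or seizure". Each is given an anticipated rate of about 1%.
- **The monitoring sentence has three.** "A heuristic approach is used to monitor each of the three toxicities in the TXA group".
- **The trigger uses both readings in one sentence.** "For each toxicity, starting from the 3rd patient, if the number of patients with any toxicity is equal to or larger than 3", then "the study accrual will be paused and amendments to the protocol will be discussed with the IRB".
- **The operating characteristic is stated once.** "This monitoring rule yields the largest type-I error rate 0.044 when the 20th" patient is affected. The same sentence describes that case in the singular: "patient show the toxicity (the 20th patient and any two previous patients in the TXA group".

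The 20 patients are the 19 evaluable in the TXA arm plus one removed for missing the second dose. No combined 4% rate appears anywhere, and the text does not say which three toxicities are meant.

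**The concern.** Three of the phrases describe a separate count for each toxicity: the one announcing that each of three is monitored, the opening of the trigger, and the singular in the error sentence. One phrase, the count of patients with *any* toxicity, describes a single pooled count. The stated error rate can belong to only one of these rules.

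This is the only numerical trial-level safety trigger in the documents. Section 9.4 has the DSMB review safety every six months but gives it no boundary. If three TXA patients each had a different toxicity, the study team would have to decide what the rule means after seeing the events. The word *three* adds a further risk. Section 8.2.1 lists exactly three unacceptable toxicities (kidney injury, anaphylaxis, seizure) and omits thrombosis. A reader who resolves the count from there would leave out the event that Section 4.4.1 identifies as a heightened risk in these children.

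**Working it through.** **Inputs (Section 11.1).** n = 20 TXA patients; threshold r = 3; anticipated rate 1% per toxicity; four toxicities listed, three said to be monitored; stated error 0.044.

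**Formula.** The threshold is a fixed count, so accrual has been paused by patient 20 exactly when at least three of the 20 are affected. Repeated looks add nothing:

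P(pause) = P(X ≥ 3) = 1 − (1−p)^20 − 20·p·(1−p)^19 − 190·p²·(1−p)^18

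Summing the first-crossing probabilities from patient 3 to patient 20 gives the same values.

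**Step 1: reproduce 0.044.** With p = 4 × 1% = 0.04: 1 − 0.4420 − 0.3683 − 0.1458 = 0.0439, which rounds to the stated figure. Solving the formula for 0.044 gives p = 0.0401, with 0.0399 to 0.0402 covering rounding. The figure therefore implies a 4% rate.

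**Step 2: the per-toxicity rule.** With p = 0.01: 1 − 0.8179 − 0.1652 − 0.0159 = 0.0010. Assuming independent toxicities, the chance that at least one of several separate rules fires is:

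- four rules: 1 − (1 − 0.0010)^4 = 0.0040
- three rules: 1 − (1 − 0.0010)^3 = 0.0030

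**Step 3: summary at the anticipated rates.**

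| Rule, 3 or more of 20 | Null rate | Type-I error |
|---|---|---|
| One toxicity | 1% | 0.0010 |
| Any of three separate rules | 1% each | 0.0030 |
| Any of four separate rules | 1% each | 0.0040 |
| Three pooled | 3% | 0.0210 |
| Four pooled | 4% | 0.0439 |

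Comparing overall error for four toxicities, 0.0439 / 0.0040 is about 11.

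**Step 4: other readings of the closing sentence.** At 1%, the chance that the third event falls exactly on patient 20 is 0.00014. The chance that at least two of the previous 19 are affected, given that the 20th is, is 0.015. Neither gives 0.044.

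**Step 5: does the choice of rule matter?** The true rates below are assumptions for illustration, with independent toxicities.

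| Assumed true rates | Four separate rules | Pooled rule |
|---|---|---|
| 3% each | 0.08 | 0.41 |
| 5% each | 0.27 | 0.75 |
| Thrombosis 10%, others 1% | 0.33 | 0.47 |
| Thrombosis 15%, others 1% | 0.60 | 0.71 |

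The gap is large when harm is spread over several toxicities and modest when it sits in one.

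**The case against.** The strongest reply is that the operative count is of patients with *any* toxicity. That is pooled language, and under that reading with four toxicities 0.044 is correct. The defect would then be loose drafting, and the printed figure itself shows which rule was meant. Much of this stands: the text is contradictory rather than purely per toxicity, and the pooled rule is the likely intention. It does not clear the paragraph. Under the pooled reading the count of three, the opening of the trigger sentence and the singular in the error sentence are all wrong, and pooling three gives 0.021. A clinician would have to work out a binomial tail to discover the intended rule.

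A second reply concerns the consequences. The rule is described as heuristic and leads to a pause, not termination. The DSMB reviews safety every six months, and Section 9.3.1 requires reporting within seven days of unanticipated fatal or life-threatening events possibly due to treatment. These safeguards limit the harm, but none supplies a numerical trigger.

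A third reply is about how the difference is measured. At the anticipated rates the separate rules omit about 90% of the pauses that the pooled rule would call: (0.0422 − 0.0040) / 0.0422, using the patient-level rate 1 − 0.99^4 = 3.94%. Those pauses are false alarms by definition, so this shows how different the rules are, not how much safety is lost. Step 5 is the better guide to safety, and it depends on assumed rates. The largest gaps there need all four rates to rise together.

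**Conclusion.** The concern holds. No single reading makes the whole paragraph true. The stated 0.044 is the error of a rule pooling four toxicities at 4% in 20 TXA patients. The predominantly per-toxicity wording describes rules with error 0.0010 each, or about 0.0040 overall. The overall figures assume independent toxicities; the single-rule and pooled binomial figures need only the stated event rates and independent patients. The 4% is a simple sum: the 3.94% patient-level rate gives 0.042, which does not change which rule the figure belongs to. Efficacy analysis and sample size are unaffected. What is affected is whether three TXA patients with different toxicities pause accrual in a trial that Section 10.2 classes as high risk for monitoring.

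**What to change.** Replace the rule with wording such as: *Accrual will be paused when 3 or more patients in the TXA group have had any of the four unacceptable toxicities (acute kidney injury, grade 3–4 anaphylaxis, thrombotic event, seizure) combined, each patient counted once; with a combined null rate of 4% and 20 patients, the type-I error is 0.044.* Change three to four, drop the opening that applies the rule to each toxicity, and remove the singular from the error sentence. Either align the list in Section 8.2.1 with this one or say why thrombosis is omitted there.

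If separate rules are intended, say so, name the toxicities, and restate the error as about 0.001 each (about 0.004 overall for four).

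The cost is a wording amendment. Under the pooled rule the threshold, the sample size and the 0.044 all stay as they are.

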11.2 Primary Objective

- 11.2.1. To evaluate the difference in intra-or post-operatively transfused blood volume (mL/kg) for patients undergoing limb salvage procedures who are randomized to receive perioperative tranexamic acid (TXA) versus placebo.

The intra-or post-operative volumes of transfused blood for both the TXA treated group and placebo group will be estimated with a two-sided 95% confidence interval. The blood volumes transfused per kilogram of body weight of the two groups (TXA vs. Placebo) will be evaluated using a two-sided student's t-test after $\log(1+x)$ transformation.

- 11.2.2. Accrual and study duration

This study will be conducted solely at St. Jude Children's Research Hospital (SJCRH). According to the historical data, during January of 2014 through December of 2017 (48 months), 39 patients underwent limb-sparing tumor resections of the proximal tibia or distal femur that met the inclusion criteria for our proposed study. These preliminary data suggest that the randomized controlled trial with 39 patients (TXA vs. Placebo) would be feasible in a 48 months period of time.

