2.2 Rationale

Children, adolescents and young adults undergoing major surgery are frequently exposed to a high risk of perioperative bleeding with concomitant requirement of blood product transfusion. This increases the risk of postoperative adverse outcomes, resulting in longer length of hospital stay and increased morbidity and mortality. The underlying mechanisms that increase the bleeding risk differ depending on the type of surgery performed. Increased fibrinolysis has been implicated as a contributing factor in excessive blood loss in pediatric spinal surgery, adult arthroplasty (TKA) and other major surgeries. Studies utilizing TXA in pediatric orthopedic surgery support its use to reduce perioperative blood loss, drain output and post-operative hematoma. 1,2,11,15

Because of the significant risks and complications associated with blood loss and allogenic transfusions, efforts to identify safe and effective ways of minimizing blood loss perioperatively are crucial. Reducing blood loss and transfusion needs minimizes post-operative complications, hospital stay length, and decreases risk of development of transfusion related complications such as allergic or transfusion reactions, transfusion-related acute lung injury (TRALI), or risk of transmission of blood borne illness^{18,19}.

Maintaining a nearer to normal Hgb and Hct allows the patient to undergo more aggressive physical therapy sooner. Higher postoperative Hgb and Hct levels promote improved wound healing as well. The use of antifibrinolytic drugs will help to improve clinical care and functional outcome of children undergoing limb salvage operations.

The administration of antifibrinolitics, such as TXA and EACA, has been shown to reduce bleeding in various surgeries including cardiac, trauma, hip, and knee arthroplasty, gynecological, and urologic procedures in adolescents and young adults.^{1,2} Since January of 2014 to December of 2017, 39 patients at our institution underwent limb-sparing tumor resections of the proximal tibia or distal femur that met the inclusion criteria for our proposed study. All 39 patients received either an intraoperative or postoperative blood transfusion. The average total blood volume transfused was 19.78 mL/kg with a standard deviation of 11.38 mL/kg. The average number of transfusions received was 2.95 with a standard deviation of 1.83. The average Estimated Blood Loss per Kilogram of Body Weight was 17.84 mL/kg with a standard deviation of 16.28 mL/kg.

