3. RESEARCH PARTICIPANT ELIGIBILITY CRITERIA AND STUDY ENROLLMENT

According to institutional and NIH policy, the study will accession research participants regardless of gender and ethnic background. Institutional experience confirms broad representation in this regard.

All clinical and laboratory studies to determine eligibility must be performed within 7 days prior to enrollment unless otherwise indicated. Laboratory values used to assess eligibility must be no older than 7 days at the start of therapy. If a post-enrollment lab

value is outside the limits of eligibility, or laboratory values are > 7 days old, then the following laboratory evaluations must be re-checked within 72 hours prior to initiating therapy: CBC with differential, PT, PTT, INR, Fibrinogen, Pregnancy Test and Comprehensive Metabolic Panel (CMP).

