11. STATISTICAL CONSIDERATIONS

11.1 Sample Size Consideration and Randomization

This study will be conducted as a randomized, placebo-controlled double-blind trial of the administration of TXA vs. placebo prior to a limb salvage procedure. The primary objective will be to evaluate if TXA will reduce the proportional blood transfusion volume and EBL. The sample size is calculated based on the hypothesis that the TXA administration will reduce the average total volume of red blood cell transfused per kilogram of body weight by 40% relative to the average total volume of red blood cells transfused of the placebo group. Our historical data should be representative of our proposed placebo group, and historically, the average total red blood cell volume transfused per kilogram of body weight is $19.78 \text{ mL/kg} \pm 11.38$. The distribution of the intra-or post-operatively transfused blood volume is normally distributed after $\log(1+x)$ transformation (mean=2.906, sd = 0.507). We use the two-sample t-test with unequal variances to access the primary objective through the $\log(1+x)$ transformation of proportional blood transfusion volume.

We calculate the sample size with the two-sided two-sample t-test with unequal variances for the $\log(1+x)$ transformation proportional blood transfusion volume. Nineteen patients in each group are sufficient to detect a 40% decrease of $\log(1+x)$ transformation of proportional blood transfusion volume (mean=2.435, sd = 0.488) with 0.8 power and type I error 0.05. It can be safely assumed that the number of patients who

do not require blood transfusion is less than 5%. Given the sample size, we do not anticipate the blood transfusion volume will have substantial ties at 0.

Randomization will be performed in the SJCRH Pharmaceutical Services Department by a pharmacist using the randomization program developed by the Department of Biostatistics.²⁶ The drug is clear and will be given IV. The people who would determine the transfusion volume are blinded to the treatment. The randomization is stratified by the variable pre-operative weight that leads to two strata: pre-operative weight > 45.2 kg and pre-operative weight <=45.2 kg, where 45.2 kg is the median of pre-operative weight in the historical control data underwent limb-sparing tumor resections of the proximal tibia or distal femur. The assignment ratio of the TXA group to the placebo group is 1:1.

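### Randomisation is stratified by weight but the primary t-test ignores the stratum; adding one model term is a cheap improvement to a valid test

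*Combined protocol and SAP*

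**What the plan says.** On allocation, Section 11.1 states: "The randomization is stratified by the variable pre-operative weight that leads to two strata", above 45.2 kg and at or below it. The cut-point was chosen because "45.2 kg is the median of pre-operative weight in the historical control data", so two strata of about equal size are to be expected. The ratio is 1:1. The section does not describe blocking within strata.

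On the analysis, Section 11.1 says "We use the two-sample t-test with unequal variances to access the primary objective", on the log(1+x) scale. Section 11.2.1 says: "The blood volumes transfused per kilogram of body weight of the two groups (TXA vs. Placebo) will be evaluated using a two-sided" Student's t-test on the same scale. Neither has a stratum term or covariate, and no treatment comparison in 11.2 or 11.3 is adjusted. Covariates appear only in the exploratory ROTEM regression (11.4.2).

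On estimation, Section 11.2.1 says: "The intra-or post-operative volumes of transfused blood for both the TXA treated group and placebo group will be estimated" with a 95% interval. That is one interval per arm. No interval for the difference between arms is mentioned, although the difference is the primary objective.

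**The concern.** Stratified allocation that balances the arms within each weight group removes between-group variation from the difference in arm means. A plain two-sample t-test still counts that variation in its standard error. If weight group is related to mL/kg transfused, the reported standard error is larger than the true sampling variability, the interval is too wide and the test rejects too rarely under the null.

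A relation is plausible. Section 6.2.1.2 sets the intra-operative transfusion volume per kilogram below 30 kg and as a whole unit above it, so mL/kg per transfusion falls with weight in the heavier patients. With only 38 evaluable patients from one centre and a 48-month accrual period, precision that costs no new data is worth having.

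**Working it through.** **Inputs.** Section 11.1 gives means of 2.906 (placebo) and 2.435 (TXA) on the log(1+x) scale, SDs of 0.507 and 0.488, 19 per arm, two-sided alpha 0.05 and power 0.8. The share of within-arm variance of log(1+mL/kg) explained by the weight stratum (R²) is not in the documents. I assume 0, 0.05 and 0.10.

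**Step 1: reproduce the plan's figure.** The difference is 2.906 − 2.435 = 0.471. The standard error is √((0.507² + 0.488²)/19) = √(0.4952/19) = 0.1614. The noncentrality is 0.471/0.1614 = 2.92, with 35.95 Welch degrees of freedom. The noncentral t distribution gives power 0.810 at 19 per arm and 0.788 at 18, so 19 per arm is confirmed.

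**Step 2: near-1:1 balance within strata.** The true SD of the unadjusted difference is about 0.1614 × √(1 − R²), while the t-test still reports about 0.162. For large samples the size is therefore roughly 2 × (1 − Φ(1.96/√(1 − R²))), which is 0.044 at R² 0.05 and 0.039 at R² 0.10. Simulation at the actual sample size (two strata of 19, split 10/9 and 9/10, results averaged over both orientations) gives:

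| | R² 0 | R² 0.05 | R² 0.10 |
|---|---|---|---|
| True SD of unadjusted difference (formula) | 0.1614 | 0.1574 | 0.1532 |
| SE reported by t-test | 0.1615 | 0.1617 | 0.1618 |
| SE reported with stratum term | 0.1617 | 0.1576 | 0.1533 |
| Size, t-test | 0.050 | 0.045 | 0.040 |
| Size, stratum term | 0.05 | 0.05 | 0.05 |
| Power, t-test | 0.811 | 0.815 | 0.820 |
| Power, stratum term | 0.809 | 0.828 | 0.848 |
| 95% CI width, t-test | 0.650 | 0.651 | 0.652 |
| 95% CI width, stratum term | 0.652 | 0.635 | 0.618 |

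The change in power is −0.2, +1.3 and +2.8 points. The interval is about 2% narrower at R² 0.05 and 5% narrower at 0.10 (0.618/0.652 = 0.948). The gain comes from reporting the right standard error: the estimate itself varies almost as much with the stratum term as without it.

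**Step 3: looser balance within strata.** If each patient were allocated independently at 1:1, the t-test would keep its size (0.050 at R² 0.10). The stratum term would then lower the true SD of the estimate, from 0.164 to 0.158 at R² 0.10, by correcting chance imbalance. If weight is not prognostic, the term costs about 1 power point in this setting.

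**Step 4: scale of the reported effect.** exp(−0.471) = 0.624 is a ratio of (1 + mL/kg). The ratio of back-transformed volumes is (e^2.435 − 1)/(e^2.906 − 1) = 10.42/17.28 = 0.603. The two are close but not the same, so a back-transformed model estimate needs the right label.

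**The case against.** The strongest case against acting is that nothing is broken. The planned test never exceeds its nominal size, and in the balanced settings of Step 2 its power stays above 0.80. The endpoint is already per kilogram, which removes part of any weight effect. The benefit depends on an R² that the documents do not give. All of this stands, and it limits the point to an improvement.

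It is also true that conservatism needs near-equal allocation within strata, which the documents do not describe. A reader might infer from the word stratified alone that the test must be conservative. Step 3 shows that this does not follow. The stratum term helps in either case if weight is prognostic, but for a different reason.

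Two further readings are tempting and are not supported:

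- *Adjust for pre-operative haemoglobin as well, since it bears on the transfusion trigger.* No figure in the documents supports a haemoglobin R², and it was not used in randomisation. If neither term is prognostic, the two together bring power to 0.794, below the stated 0.80. The value to use would also need naming, because eligibility laboratory tests may be repeated (Section 3).
- *The historical figures show that weight has no effect.* Section 2.2 gives a coefficient of variation of 1.83/2.95 = 0.620 for the number of transfusions and 11.38/19.78 = 0.575 for mL/kg. A reader might take the lower second value as a sign that heavier patients received more units, which would cancel any weight effect. These are two close sample estimates from 39 patients, and the documents do not say that those patients were transfused under the trial's rules. They do not settle the question.

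Finally, 11.1 names the unequal-variance test and 11.2.1 Student's. The names should agree, but the choice changes power by only about 0.001.

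**Conclusion.** The point holds as a low-cost improvement. The primary comparison omits the factor used to stratify randomisation, and no other part of Section 11 restores it. With near-1:1 balance within strata and a stratum R² of 0.05 to 0.10, the planned test has a true size of about 0.045 to 0.040 and forgoes about 1 to 3 power points. With looser balance, its size is correct and it forgoes a reduction in true variability instead. At R² 0 there is nothing to gain.

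The figures rest on the plan's own SDs, normal errors on the log(1+x) scale, strata of equal size and an assumed R² range. A reader might infer that the primary result would be invalid or the trial underpowered. The documents do not support that: the sample size reproduces and the direction of any error is conservative.

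**What to change.** Before unblinding, amend 11.2.1 so that the primary analysis is a linear model of log(1+mL/kg) on treatment arm and weight stratum (above 45.2 kg versus 45.2 kg or less). Report the adjusted between-arm difference with its 95% confidence interval. If it is back-transformed, label it a ratio of (1+mL/kg). Keep the unequal-variance t-test as a sensitivity analysis, under one name in 11.1 and 11.2.1. Do not add haemoglobin by default. It would also help to state in 11.1 how balance within strata is maintained, to the extent that this can be disclosed without compromising the blind.

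No new data are needed, because the stratum is known at randomisation. The cost is one degree of freedom: about 0.2 power points with balanced strata if weight is not prognostic, and about 1 point if allocation within strata is not balanced. Because Section 11 is part of the protocol, the change needs a small protocol amendment. The sample size does not change.
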